15.1 Adverse Events

Treatment-emergent adverse events (TEAEs) are those events that begin or that worsen in severity after at least one dose of the study intervention has been administered.

Adverse events related to study treatment are those events with relationship missing, unknown or related.

AEs will be coded using the most recent MedDRA version at time of database lock.

All analyses described in Section 15.1 will be based on TEAEs if not otherwise specified. The AE listings will include all AEs (whether treatment-emergent or not). Non TEAEs will be flagged in the listings.

Unless otherwise specified, TEAEs will be summarized by number and percentage of participants with the TEAE in the category of interest, by hepatic function group, primary SOC and PT in decreasing frequency.

Each participant will be counted only once within each SOC or PT. If a participant experiences more than one AE within a SOC or PT for the same summary period, only the AE with the strongest relationship or the worst severity, as appropriate, will be included in the summaries of relationship and severity.

15.1.1 All Adverse Events

Adverse event counts and participants with AEs will be summarized for each hepatic function group by SOC and preferred term. In addition, AEs will be tabulated and listed per participant and analyzed by severity and relationship to study intervention.

In case a participant has events with missing and non-missing grades, the maximum of the non-missing grades will be displayed. No imputation of missing grades will be performed.

Incomplete AE-related dates will be handled as specified in Section 9.5.

15.1.2 Adverse Events Leading to Discontinuation of Study Treatment

Since evobrutinib is administered only once in the study, discontinuation of study intervention is not applicable.

Adverse events leading to withdrawal/discontinuation from the study intervention will be listed for each participant and summarized for each treatment group by SOC and PT. Only TEAEs will be included in the tabulation.

15.2 Deaths, Other Serious Adverse Events, and Other Significant Adverse Events

15.2.1 Deaths

In case of a fatality, the cause of death is considered as the AE, and the death is considered as its outcome. A listing of all deaths occurring during the study will be presented.

15.2.2 Serious Adverse Events

A listing of all SAEs occurring during the study will be presented.

15.2.3 Other Significant Adverse Events

A listing of other significant AEs occurring during the study will be presented.

15.3 Clinical Laboratory Evaluation

The following parameters will be measured:

- **Hematology:** platelets, reticulocytes, hemoglobin, hematocrit, red blood cell count, white blood cell count with differential, mean corpuscular volume (MCV) and mean corpuscular hemoglobin (MCH).
- **Clinical chemistry:** blood urea nitrogen, creatinine, glucose, uric acid, C-reactive protein, albumin, urea, potassium, sodium, calcium, chloride, inorganic phosphate, magnesium, aspartate aminotransferase (AST), alanine aminotransferase (ALT), alkaline phosphatase (ALP), γ -Glutamyl-transferase, lactate dehydrogenase, creatinine phosphokinase, bilirubin, total protein, cholesterol, triglycerides, amylase, lipase, coagulation (INR and prothrombin time [PT]) and Thyroid stimulating hormone (TSH).
- **Urinalysis:** specific gravity, pH, glucose, protein, blood, ketones, bilirubin, urobilinogen, nitrite, leukocyte esterase and microscopic examination (if blood or protein is abnormal).
- **Drugs of Abuse and Alcohol Abuse** (Screening and Day -1 only): alcohol breath test and urine drug screen (to include at minimum: amphetamines, methamphetamines, barbiturates, ecstasy, cocaine, opiates, cannabinoids, benzodiazepines, methadone, phencyclidine, oxycodone, and tricyclic antidepressant).
- **Serum Pregnancy Test** (Screening, Day -1 and Follow-up/Discontinuation only).
- **Other:** FSH and estradiol (as needed if not a WOCBP only).
- **Other:** serum human chorionic gonadotropin (hCG) pregnancy test (as needed for a WOCBP).

- **Other:** urine microscopy, only if blood, protein, nitrite, or leukocyte esterase are positive on the dipstick
- **Serology:** HIV I and II antibodies, hepatitis B surface antigen, hepatitis B core antibody, hepatitis C antibody and Quantiferon® Test.

Safety laboratory parameters will be listed for each participant including changes from baseline and flags for measurements outside the reference ranges, where applicable. Laboratory parameters (hematology, coagulation and clinical chemistry) will be summarized by time point including both absolute values and changes from baseline. Urinalysis parameters will be listed.

Values below the detection limit will be imputed by half of the detection limit.

In case just a text value with an “> x” is reported it will be analyzed as +1 significant digit, e.g “> 7.2 mmol” will be analyzed as 7.3.

15.4 Vital Signs

Vital signs will be measured in a semi-supine position after 5 minutes rest and will include tympanic temperature, systolic and diastolic blood pressure, pulse rate and respiratory rate. One pulse and three blood pressure measurements will be taken. The average of the three blood pressure readings will be recorded in the CRF.

Vital signs parameters will be listed for each participant including changes from baseline and flags for measurements outside the reference ranges, where applicable. Vital signs parameters will be summarized by hepatic function group and time point including both absolute values and changes from baseline.

15.5 Other Safety or Tolerability Evaluations

Single 12-lead ECGs will be obtained using an ECG machine that automatically calculates the heart rate and measures PR, QRS, QT, and QTc intervals. ECG assessments will be done after 5 minutes rest in supine position.

12-lead ECG parameters will be listed for each participant including changes from baseline and flags for measurements outside the reference ranges, where applicable. 12-lead ECG parameters will be summarized by hepatic function group and time point including both absolute values and changes from baseline. Clinically noteworthy ECG findings for individual participants will be listed as appropriate.

15.6 COVID-19 Impact

A listing of all participants affected by the COVID-19 related study disruption (e.g. AEs/SAEs, missed visit, missed dose, treatment/study discontinuation, protocol deviation including minor, screen failure, etc.) will be provided.

16 Analyses of Other Endpoints/Estimands

16.1 Pharmacokinetics

16.1.1 Descriptive Statistics of PK Concentration Data

PK measurements will be descriptively summarized using: number of non-missing observations (n), arithmetic mean (Mean), standard deviation (SD), coefficient of variation (CV%), minimum (Min), median (Median), 25th percentile (Q1) and 75th percentile (Q3), and maximum (Max).

Descriptive statistics will only be calculated for n>2 in which a measurement of <LLOQ represents a valid measurement.

Descriptive statistics of PK concentration data will be calculated using values with the same precision as the source data and rounded for reporting purposes only.

The following conventions are applied for reporting descriptive statistics of PK concentration data:

- Mean: 3 significant digits
- SD: 4 significant digits
- Min: 3 significant digits
- Median, Q1, Q3: 3 significant digits
- Max: 3 significant digits
- CV%: 1 decimal digit

16.1.2 Descriptive Statistics of PK Parameter Data

PK parameter data will be descriptively summarized using: number of non-missing observations (n), arithmetic mean (Mean), standard deviation (SD), minimum (Min), median (Median), 25th percentile (Q1) and 75th percentile (Q3), maximum (Max), geometric mean (GeoMean), and the geometric coefficient of variation (GeoCV%). For time to reach maximum observed concentration (t_{max}) and time of the last quantifiable concentration (t_{last}), only n, Min, Median, and Max will be reported.

Descriptive statistics will only be calculated for a PK parameter when n>2.

PK parameters read directly from the measurements (i.e. C_{max}) will be reported with the same precision as the source data. All other PK parameters will be reported to 3 significant figures. In export datasets, as well as in the SDTM PP domain, PK parameters will be provided with full precision and will not be rounded. Descriptive statistics of PK parameter data will be calculated using full precision values and rounded for reporting purposes only.

The following conventions are applied for reporting descriptive statistics of PK parameter data:

- Mean: 3 significant digits
- SD: 4 significant digits
- Min: 3 significant digits
- Median, Q1, Q3: 3 significant digits
- Max: 3 significant digits
- GeoMean: 3 significant digits
- GeoCV, CV%: 1 decimal digit
- 95% CI: 3 significant digits

16.1.3 General Specifications for PK Concentration and PK Parameter Data

Pre-dose samples that occur before the first drug administration will be assigned a time of 0 hours, as if the sample had been taken simultaneously with the study drug administration.

Values below the lower limit of quantification of the assay (LLOQ) will be taken as zero for summary statistics of PK concentration data, PK parameter estimation (e.g. AUC) and for graphical presentations. It is expected that samples with concentrations above the upper limit of quantification (ULOQ) will be diluted and retested.

Missing concentrations (e.g. no sample, insufficient sample volume for analysis, no result or result not valid) will be reported and used generally as “N.R.”. A participant who withdraws prior to the last planned observation will be included in the analyses up to the time of discontinuation.

Samples that are collected outside the specified time windows specified in the Clinical Trial Protocol (CTP) will be included in the PK parameter estimation (NCA) but will be excluded from the concentration summary and mean concentration plots.

PK concentrations which are erroneous due to a protocol violation (as defined in the CSP), sampling processing or analytical error (as documented in the bioanalytical report) may be excluded from the PK analysis if agreed by the Sponsor. In this case the rationale for exclusion must be provided in the CSR. Any other PK concentrations that appear implausible to the Clinical Pharmacologist/Clinical PK/PD Scientist will not be excluded from the analysis. Any implausible data will be documented in the CSR.

Any PK concentrations or PK parameters excluded from summary statistics will be included in subject listings and flagged; a reason for exclusion will be detailed in the CSR (e.g. a footnote or a table of exclusions). Any flags should be included in the study specific SDTM and ADaM data sets.

PK concentrations and PK parameters excluded from summary statistics will not be included in individual and mean figures. Mean plots will only contain averages when N>2.

If the actual time of sample collection deviates from the protocol defined time interval the concentration will be flagged and excluded from the summary statistics.

16.1.4 Estimation of Pharmacokinetic Parameters

The following PK parameters will be determined where possible from the plasma concentrations of evobrutinib using noncompartmental methods and the validated software program Phoenix WinNonlin (Certara, Version 8.1 or higher).

The following pk parameters will be calculated where appropriate:

Parameter	Units ^a	Definition
AUC _{0-t_{last}}	h*ng/mL	area under the concentration-time curve from time 0 to the time of the last sampling time (t_{last}) at which the concentration is at or above the lower limit of quantification ^b
AUC _{0-∞}	h*ng/mL	area under the concentration-time curve from time 0 extrapolated to infinity ^c
AUC ₀₋₁₂	h*ng/mL	The area under the concentration-time curve (AUC) from time 0 to 12 hours postdose.
AUC ₀₋₂₄	h*ng/mL	The area under the concentration-time curve (AUC) from time 0 to 24 hours postdose
%AUC _{extra}	%	percentage of AUC due to extrapolation from the last quantifiable concentration to infinity
C _{max}	ng/mL	maximum observed concentration
t _{max}	h	time of the maximum observed concentration
t _{last}	h	time of the last quantifiable concentration
t _{1/2}	h	apparent terminal elimination half-life
CL/f	mL/min	apparent total clearance
V _z /f	L	apparent volume of distribution during the terminal phase
f _u	%	free or unbound fraction of evobrutinib
AUC _{0-∞,u}	h*ng/mL	unbound AUC _{0-∞} ^d
C _{max,u}	ng/mL	unbound C _{max} ^d
CL _u /f	mL/min	unbound apparent total clearance ^d

a Units are based on concentration units (provided by the bioanalytical lab or preferred units for presentation of PK parameters) and dose units used in the study.

b Area under the concentration-time curve will be calculated using the linear trapezoidal rule for increasing concentrations and the logarithmic rule for decreasing concentrations (linear up/log down rule).

c Based on the last predicted quantifiable concentration

d Calculated as the product of the bound parameter and the mean free fraction for that participant

Additional PK parameters may be determined where appropriate.

PK parameters will be calculated using the actual elapsed time since dosing, given with a precision of 14 significant digits or the SAS format Best12. In cases where the actual sampling time is missing, calculations will be performed using the scheduled time. Otherwise, there will be no further imputation of missing data.

Free (unbound) fraction will be calculated as free concentration/total concentration. For each participant, 3 samples will be analysed to determine a percent of free fraction (unbound) evobrutinib. The values from these samples, if measurable, will be used to calculate a mean free fraction, presented as percentage. The percentage free will be divided by 100% to calculate unbound PK parameters.

The parameters C_{max} , t_{last} , and t_{max} will be obtained directly from the concentration-time profiles. If C_{max} occurs at more than 1 timepoint, t_{max} will be assigned to the first occurrence of C_{max} .

Partial areas should be calculated using the nominal dosing interval. The actual dosing interval calculated from the CRF should not be used. However, actual times for partial AUC intervals may be used if the sample was taken within +/-10% of the protocol defined time, and the partial area would not be calculable using scheduled time.

The regression analysis should contain data from at least 3 different time points in the terminal phase consistent with the assessment of a straight line on the log-transformed scale. Phoenix WinNonlin “best fit” methodology will be used as standard. However, in some cases, further adjustment may be made by the pharmacokineticist, if warranted, after agreement with the Sponsor. The last quantifiable concentration should always be included in the regression analysis, while the concentration at t_{max} and any concentrations <LLOQ which occur after the last quantifiable data point should not be used.

If $\%AUC_{extra}>20\%$ and/or the coefficient of correlation (Rsq adj) of λ_z is <0.8 and/or the observation period over which the regression line is estimated is less than twofold the resulting $t_{1/2}$, the rate constants and all derived parameters (e.g. $t_{1/2}$, $AUC_{0-\infty}$, CL/f etc.) will be listed, flagged and included in the parameter outputs and may be excluded from the descriptive statistics. Any flags will be included in the study specific SDTM/ADaM and the exclusion of parameters agreed with the sponsor.

In the case that profiles have a measurable pre-dose concentration less than or equal to 5% of its C_{max} value, the participant’s data without any adjustments will be included in all PK measurements and calculations. If the pre-dose value is greater than 5% of the C_{max} , the participant will be dropped from all PK evaluations. However, this participant’s data will be flagged and reported.

The following PK parameters will be calculated for diagnostic purposes and listed, but will not be summarized:

Parameter	Units	Definition
λ_z	1/h	apparent terminal elimination rate constant
λ_z up	h	first time point of the time interval of the log-linear regression to determine λ_z .
λ_z low	h	last time point of the time interval of the log-linear regression to determine λ_z .
N_λ	NA	number of data points included in the log-linear regression
λ_z Span Ratio	NA	time period over which λ_z was determined as a ratio of $t_{1/2}$
Adjusted Rsq	NA	goodness of fit statistic (adjusted Rsq) for calculation of λ_z .

Where possible, the span of time used in the determination of λ_z (ie, the difference between λ_z Upper and λ_z Lower) should be ≥ 2 half-lives. If the λ_z Span Ratio is < 2 , the $t_{1/2}$ values will be flagged and the robustness of the estimates discussed in the CSR.

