## 8.5 Pharmacokinetics

The following PK parameters will be calculated from the individual plasma concentration-time data, when appropriate:

| Symbol                                      | Definition   |
|---|--|
| AUC 0-tlast           | The area under the concentration-time curve (AUC) from time zero (= dosing time) to the last sampling time ( $t_{last}$ ) at which the concentration is at or above the lower limit of quantification. Calculated using the mixed log-linear trapezoidal rule (linear up, log down). |
| AUC 0-12 and AUC 0-24 | The area under the concentration-time curve (AUC) from time zero (= dosing time) to 12 or 24 hours at which the concentration is at or above the lower limit of quantification. Calculated using the mixed log-linear trapezoidal rule (linear up, log down).                        |
| AUC 0-∞                          | The AUC from time zero (dosing time) extrapolated to infinity, based on the predicted value for the concentration at $t_{last}$ , as estimated using the linear regression from $\lambda_z$ determination. $AUC_{0-∞} = AUC_{0-t_{last}} + C_{last\ pred} / \lambda_z$ .             |
| C max                            | Maximum observed concentration.  |
| t max                            | The time to reach the maximum observed concentration collected during a dosing interval (i.e., 1 st occurrence in case of multiple/identical C max values).  |
| t 1/2                            | Apparent terminal half-life. $t_{1/2} = \ln (2) / \lambda_z$ .   |

| Symbol               | Definition  |
|----------------------|---|
| CL/F                 | Apparent total plasma clearance after oral administration.
$CL/F = \text{Dose}_{\text{p.o.}} / \text{AUC}_{0-\infty}$ .  |
| Vz/F                 | Apparent volume of distribution during terminal phase after oral administration.
$V_z/F = \text{Dose} / (\text{AUC}_{0-\infty} * \lambda_z)$ following single dose.  |
| f u       | Free or unbound fraction of evobrutinib calculated as free concentration/total concentration (For each participant, 3 samples will be analysed to determine a percent of free fraction or unbound evobrutinib. The values from these samples if measurable will be used to estimate a mean percentage). |
| AUC 0-∞,u | Calculated as f u * AUC 0-∞   |

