| C max, u  | Calculated as f u * C max   |
| CL u /F   | Calculated as Dose p.o. / AUC 0-∞,u   |

Whole blood samples of approximately 2 mL will be collected for measurement of plasma concentrations of evobrutinib. Collection times are specified in the SoA (Section 1.3). The actual date and time (24-hour clock time) of each sample will be recorded to calculate actual time elapsed since the prior dose administration. The sampling timing may be altered during the study based on newly available data (e.g., to obtain data closer to the time of peak plasma concentrations) to ensure appropriate monitoring.

The quantification of evobrutinib in plasma will be performed using a validated LC-MS/MS assay. Concentrations will be used to evaluate the PK of evobrutinib. The free fraction of evobrutinib sample will not be drawn separately but will be analyzed from the PK back up samples at 1.5, 4 and 12 hours.

Remaining samples collected for analyses of evobrutinib concentrations may also be used to evaluate safety or PD aspects related to concerns arising during or after the study. Full details of the bioanalytical methods will be described in a separate bioanalytical report.

Details on processes for collection and handling of these samples are in the Laboratory Manual. Retention time and possible analyses of samples after the End of Study are specified in the respective ICF.

PK parameters will be derived using noncompartmental methods with the validated computer program Phoenix® WinNonlin® (version 6.4 or higher; Certara, L.P., Princeton, New Jersey, USA).

The exact date/time of sample collection and drug administration (24-hour clock time) must be recorded in the eCRF and will be used in the calculation of PK parameters. The accepted time deviations from planned PK times that will not be considered a protocol violation are listed below:

[figure not shown]
| Procedure | Time Point (Relative Time) | Window Allowance |
|-----------|----------------------------|------------------|
| PK        | Predose                    | - 60 min         |
|           | 0.25 to 1 h postdose       | - 2 / + 2 min    |
|           | > 1 h to 12 h postdose     | - 5 / + 5 min    |
|           | > 12 h to 32 h postdose    | - 15 / + 15 min  |

The predose sample will be considered as if it had been taken simultaneously with the administration of study intervention.

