### 9.4.3 Other Analyses

Details on the PK analyses will be specified in the Integrated Analysis Plan that will be finalized before database lock. Integrated analyses across studies, such as the population PK analysis and PD analyses will be presented separately from the main clinical study report (CSR).

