SDTM	Study Data Tabulation Model
SOC	System Organ Class
t _{1/2}	Apparent Terminal Elimination Half-life
TEAE	Treatment-Emergent Adverse Event
t _{last}	Time of the Last Quantifiable Concentration
t _{max}	Time of the Maximum Observed Concentration
TSH	Thyroid Stimulating Hormone
UNK	Unknown
V _{z/f}	Apparent Volume of Distribution During the Terminal Phase
WHO-DD	World Health Organization Drug Dictionary
WOCBP	Woman of Childbearing Potential

3**Modification History**

Unique Identifier for Version	Date of IAP Version	Author	Changes from the Previous Version
1.0	02 February 2021	PPD	Initial version

4**Purpose of the Integrated Analysis Plan**

The purpose of this IAP is to document technical and detailed specifications for the final analysis of data collected for protocol MS200527_0059. Results of the analyses described in this IAP will be included in the Clinical Study Report (CSR). Additionally, the planned analyses identified in this IAP may be included in regulatory submissions or future manuscripts. Any post-hoc, or unplanned analyses performed to provide results for inclusion in the CSR but not identified in this prospective IAP will be clearly identified in the CSR.

The IAP is based upon Section 9 of the study protocol and protocol amendments and is prepared in compliance with ICH E9. It describes analyses planned in the protocol and protocol amendments.

All final, planned analyses identified in the clinical study protocol will be performed only after the last participant has completed the last visit, i.e. Follow-up/Discontinuation visit, with all study data in-house, all data queries resolved, and the database locked.

5**Objectives and Endpoints**

Objectives	Endpoints	IAP section
Primary		
To investigate the PK of evobrutinib after a single dose to participants with hepatic impairment compared to participants with normal hepatic function	AUC _{0-∞} , and C _{max}	16.1
Secondary		
To assess the safety and tolerability of evobrutinib when administered as a single dose to participants with normal hepatic function and with impaired hepatic function	Occurrence of treatment-emergent adverse events (TEAEs), changes from Baseline in laboratory safety tests, 12-lead ECG morphology and time intervals (PR, QRS, RR, QT, and QTcF), and vital signs from time of first dose to the End of Study	15

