To characterize the effect of hepatic function on the PK of evobrutinib through secondary PK endpoints	t _{max} , t _{1/2} , AUC ₀₋₁₂ and AUC ₀₋₂₄ , AUC _{0-t_{last}} , CL/f, Vz/f, unbound fraction in plasma (f _u), AUC for unbound drug from time zero to infinity (AUC _{0-∞,u}), unbound C _{max} (C _{max,u}), and unbound apparent oral clearance (CL _{u,f})	16.1
Tertiary/Exploratory		
Not applicable		

6 Overview of Planned Analyses

The following analysis is planned for this trial:

- Primary analysis of trial to be performed only after the last participant has completed the last visit, i.e. Follow-up/Discontinuation visit, with all study data in-house, all data queries resolved, and the database locked.

Statistical analyses will be performed on the basis of Clinical Data Interchange Standards Consortium (CDISC) Study Data Tabulation Model (SDTM) data. These SDTM data contain as clean as possible eCRF data as well as external data including pharmacokinetic data.

There are no planned formal interim analyses.

A data review meeting will be held prior to any database lock. In addition, no database can be locked until this IAP has been approved (except for emergency).

7 Changes to the Planned Analyses in the Clinical Study Protocol

There are no changes to the analyses planned per protocol.

8 Analysis Sets and subgroups

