16.1.5.3 Primary Endpoint Analyses

Pharmacokinetic analyses will be done on the PK analysis population and according to the as-treated principle.

An analysis of variance (ANOVA) model including hepatic function group as a fixed effect will be applied to log-transformed PK parameters $AUC_{0-\infty}$, and C_{max} of evobrutinib of the hepatic impairment groups (Child-Pugh class A and Child-Pugh class B) and control group (Normal Hepatic Function). Separate models will be fitted for the comparison between the hepatic impairment groups (Child-Pugh class A and Child-Pugh class B) and the control group (Normal Hepatic Function). For each parameter, differences between the hepatic impairment groups and the control group will be estimated on the log scale (group mean ratio) together with corresponding 90% confidence intervals (CIs). The geometric least square means together with corresponding 95% CIs by hepatic function group will also be estimated. Point estimates and CIs will be back-transformed to the original scale.

The relationship between $AUC_{0-\infty}$ and C_{max} of evobrutinib and the hepatic function parameters (e.g., albumin-bilirubin score and De Ritis ratio as continuous variable) at baseline (arithmetic mean of screening and Day -1 values) will additionally be explored with a linear regression.

For secondary PK endpoints such as CL/f , $AUC_{0-\infty,u}$, $C_{max,u}$, and CL_u/f , the same ANOVA and linear regression analyses like for the primary endpoints will be performed.

17

References

Not applicable.

18 Appendices

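### SAP footnote d multiplies CL/f by the free fraction to get unbound clearance, whereas the protocol's formula divides by it

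*SAP*

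**What the plan says.** Protocol Section 8.5 defines CL/F as oral dose over AUC0-∞. It defines AUC0-∞,u as the free fraction times AUC0-∞ ("Calculated as f u * AUC 0"-∞) and Cmax,u in the same way. For unbound clearance it gives "Calculated as Dose p.o. / AUC 0-∞,u".

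SAP Section 16.1.4 lists the same parameters. Its footnote d is attached to AUC0-∞,u, Cmax,u and CLu/f, and reads "Calculated as the product of the bound parameter and the mean free fraction for that participant". The only other SAP instruction on the unbound parameters comes later in that section: "The percentage free will be divided by 100% to calculate unbound PK parameters". This sets the scale of fu but does not say whether fu multiplies or divides.

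SAP Section 7 states: "There are no changes to the analyses planned per protocol". For secondary PK endpoints, with CLu/f named among them, SAP Section 16.1.5.3 says that "the same ANOVA and linear regression analyses like for the primary endpoints will be performed".

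**The concern.** An exposure measure scales up with the free fraction. A clearance, being dose over exposure, scales down with it. One footnote that prescribes a product for all three parameters therefore cannot be right for all three. The row for CLu/f carries the footnote explicitly, and no other SAP text gives a formula for it.

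The protocol leaves the detail to the SAP ("Details on the PK analyses will be specified in the Integrated Analysis Plan that will be finalized before database lock"), so someone programming from the SAP alone would reach the inverted formula. CLu/f is a named secondary endpoint that is listed, summarised, compared between groups with 90% confidence intervals and regressed on hepatic function scores. All of these outputs would be wrong. The report would then hold two unbound results that contradict each other, AUC0-∞,u and CLu/f, in a study meant to inform dose-adjustment recommendations.

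**Working it through.** The plan states no figure to reproduce here, so the check is algebra followed by illustration.

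**Inputs from the documents:** dose 30 mg for everyone (protocol Section 6.1); the formulas in protocol Section 8.5; SAP footnote d; an expected CV of 30% to 60% for AUC and Cmax (protocol Section 1.1); 8 participants per group; an approximately 3-fold fall in clearance with CYP3A4 inhibitors (protocol Section 4.2), which the protocol uses to anticipate the effect of hepatic impairment.

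**Not in the documents, so assumed:** values of fu, and the ratio of fu between groups.

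**Step 1: the two formulas.**
- Protocol: CLu/F = Dose / AUC0-∞,u = Dose / (fu × AUC0-∞) = (CL/F) / fu.
- SAP footnote d: CLu/f = (CL/f) × fu.
- SAP divided by protocol = fu².

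**Step 2: consequences that need no assumed values.**
- Each participant's CLu/f is wrong by the factor fu².
- For any fu below 1, the SAP rule puts unbound clearance below total clearance. Under the protocol's definitions it must be above.
- CLu/f × AUC0-∞,u should equal the dose. Under the SAP rule it equals (Dose/AUC0-∞) × fu × fu × AUC0-∞ = fu² × 30 mg.
- Let R be the impaired-to-normal ratio of total clearance and r the ratio of geometric mean fu. The correct CLu/f ratio is R/r, the SAP rule gives R × r, and the error factor is r². The point estimate is right only if r = 1.
- Correctly, log CLu/f is log CL/f minus log fu. Under the SAP rule it is log CL/f plus log fu. A regression slope is therefore wrong by twice the slope of log fu.

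**Step 3: size per participant (fu assumed).**

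| Assumed fu | SAP / correct = fu² | SAP value too small by | CLu/f × AUC0-∞,u under SAP |
|---|---|---|---|
| 5% | 0.0025 | 400-fold | 0.0025 × 30 = 0.075 mg |
| 20% | 0.04 | 25-fold | 0.04 × 30 = 1.2 mg |

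**Step 4: size for the group ratio (R = 1/3, r assumed).**

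| fu ratio r | Correct R/r | SAP R × r | Error r² |
|---|---|---|---|
| 1.0 | 0.33 | 0.33 | 1.00 |
| 1.1 | 0.30 | 0.37 | 1.21 |
| 1.25 | 0.27 | 0.42 | 1.56 |
| 1.5 | 0.22 | 0.50 | 2.25 |

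If total clearance did not change (R = 1) and r were 1.5, the correct ratio would be 1/1.5 = 0.67 and the SAP rule would give 1.50, so the direction reverses. For r above 1, this happens whenever R lies between 1/r and r.

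**Step 5: comparison with the study's precision.** With 8 against 8, and assuming CLu/f has the CV expected for AUC, the 90% CI half-width as a factor is exp[t(0.95; 14 df) × √ln(1 + CV²) × √(2/8)]. This is 1.295 at CV 30% and 1.630 at CV 60%. The error r² exceeds it once r is above √1.295 = 1.138 or √1.630 = 1.277. With 12 controls, which the protocol allows, the half-widths are about 1.26 and 1.55, and the thresholds about 1.12 and 1.25.

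**The case against.** The inversion itself is not in dispute. The case on the other side is that it matters little and would probably be caught.

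- **Limited scope.** The study is descriptive, and its primary endpoints are AUC0-∞ and Cmax, which are unaffected. AUC0-∞,u and Cmax,u are correct. At a single fixed dose the CLu/f ratio adds nothing to the AUC0-∞,u ratio, and the error can be put right at any time from stored data. All of this stands and limits the harm. It does not make the prespecified formula correct.
- **The protocol would prevail.** With no changes declared in SAP Section 7, a programmer could fall back on the explicit protocol formula. The footnote also refers to a bound parameter that the table does not contain, so it needs interpreting. That outcome is possible, but the SAP does not direct it. The no-change statement is equally evidence that the conflict went unnoticed.
- **Is the protocol formula out of the SAP's view?** The SAP says "The IAP is based upon Section 9 of the study protocol and protocol amendments", and the correct formula is in Section 8.5. This carries no weight, because the SAP's PK text plainly draws on Section 8.5 as well.
- **The error would be conspicuous.** Every CLu/f would fall below CL/f in the same listing. That is true, but the SAP specifies no check that would look for it.
- **The sizes are hypothetical.** No fu value or expected fu difference is given, the 3-fold fall comes from an inhibitor study, and the precision comparison assumes a CV. This is fair. The tables are illustrations, and the conclusion rests on the algebra alone.

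**Conclusion.** The concern holds. For CLu/f, SAP footnote d contradicts protocol Section 8.5 and is inverted, and nothing else in the SAP corrects it. The error is fu² per participant and the squared fu ratio between groups; these results follow from the documents' own definitions. How large that is in practice depends on fu, which the documents do not give. The group ratio comes out right only if geometric mean fu is the same in both groups, and the protocol does not assume this, since it measures fu in every participant. The damage is confined to one secondary endpoint and depends on the footnote being programmed literally. Because the instruction is wrong as written and feeds an inferential analysis, it must be corrected.

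**What to change.** In SAP Section 16.1.4:

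- Limit footnote d to AUC0-∞,u and Cmax,u, and replace the word *bound* with *total*.
- Add a footnote e for CLu/f: dose divided by AUC0-∞,u, equivalently CL/f divided by the participant's mean free fraction expressed as a fraction. This restores the formula in protocol Section 8.5.
- Bring the programming specification into line, and add a check that CLu/f × AUC0-∞,u equals 30 mg after unit conversion for every participant with both values.

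The cost is one footnote, the matching specification and one programmed check. No new data are needed and nothing in the design changes.
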